Only research staff cleared to obtain written consent will escort participants to a private room in Gwynn Hall, where all screening and consenting will take place. After participants have cleared the initial screening checklist (the PAR-Q form and inclusion/exclusion criteria), research staff will deliberately and clearly explain each aspect of the informed consent. Participants will be encouraged to ask questions and will be reminded of the voluntary nature of their participation prior to signing the informed consent form. Signed informed consents will be collected and securely stored in [name] office. At this time, participants will also be given an additional copy of the informed consent for future reference.

Number of Subjects

Using G*Power (V3.1) sample size calculations were completed using estimated and calculated effect sizes from previously published SSSH research⁷⁻⁹. Estimated low and medium effect sizes resulted in a sample size ranging from 12-55. Calculated effect sizes for the 30 second sit to stand (balance), DXA (body composition), and the Self Administered Gerocognitive Examination (cognitive function) resulted in a sample size ranging from 9 to 43. We believe nearly 50 participants total are needed to reach statistical power for this study; however, assuming 15% attrition rates, 60 participants (up to 20 per group) will be recruited for the study.

Study Procedures/Design/Treatment Plan

Participants who chose to enroll will be required to provide approximately five hours of their time total, in addition to intervention exercise activities. The first visit will consist of the initial screening form and the informed consent, followed by a facility tour, and familiarization of the testing procedures and will take one hour. The second and third visits are identical in procedure and time required and will consist of a urine sample, blood draw, anthropometrics, DXA scans, and functional performance assessments, and questionnaires. These two visits lasting 2 hours each will occur immediately before and after the eight week intervention period. Each visit and all questionnaires and procedures are explained in greater detail below. This organizational timeline of study activities will also be made available for participants.

Visit I

Location: The first visit will take place in the Exercise Physiology Laboratory in Gwynn Hall, subsequent tours of McKee Gymnasium may also occur.

Duration: 1 hour

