During the first visit to campus participants will go over the initial screening form which includes the Physical Activity Questionnaire (PAR-Q), a risk assessment for chronic disease characteristics that may increase risk of exercise injury, and the inclusion and exclusion criteria. If participants are cleared they will then be given the informed consent and allowed ample time to ask questions about the study requirements. All possible precautions will be taken to avoid inadvertent coercion in the recruitment process. The research team will stress that participation is completely voluntary and can be terminated at any time for any reason.

Once participants clear the initial screening process and sign the informed consent (a copy of the informed consent will be provided to the participant at this time), participants will be given a tour of the McKee Gymnasium where they will become familiar with all testing procedures. Qualified subjects will be scheduled for Visit II.

Visits II & III

Location: The first part of these visits will take place in the Exercise Physiology Laboratory in Gwynn Hall, followed by function performance testing in McKee Gymnasium.

Duration: 2 hours

The methods for Visit II and Visit III are identical and will occur the week prior to the SSSH intervention beginning and the week after the intervention is over. Both of these visits will include a urine sample, blood draw, and DXA scans followed by functional performance testing and questionnaires. Questionnaires include pre/post General Health Survey, the Pittsburgh Sleep Quality Index survey, and the Self Administered Gerocognitive Examination. Each procedure is described in detail below.

Anthropometrics: Participant height and weight will be measured and their BMI (kg/m²) will be calculated. Participant resting blood pressure (mmHg) will also be taken.

Urine sample: Participants will be asked to provide a urine sample to ensure proper hydration for DXA scans.

Blood Draw: 7-10 ml of blood will be drawn from the subject using a butterfly needle and vacutainer. These samples will be allowed time to clot and then spun in serum separator tubes. Serum will then be aliquotted into microtubes and stored till bone turnover assay can be ran. Samples will be stored in Gwynn Hall and analyzed at the Missouri Orthopaedic Institute.

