Timed up and go (TUG) and 30 second sit to stand (30STS) Tests: Both of these dynamic tests are used to assess a participant's balance and lower body strength. The TUG requires participants to rise from a seated position, walk around a cone 8 ft away and return to their seated position. Participants will be timed during this test. The 30STS has two commonly reported variations. First, is how quickly a participant can rise from a seated position, fully stand, and return to the seated position five times. The second iteration is how many times can a participant complete this same complete motion in 30 seconds. We will measure both. Additionally the 30STS will be completed on two force plates to better understand lower body power and balance. Participants will perform the same test after completion of intervention period.

Once participants have enrolled in the study [name] will randomize the participants into either the experimental group, walking group, or sedentary group. They will be notified of their assignment based on their preferred communication method by [name].

Participants who are assigned the SSSH program will engage in eight weeks of strength training and will be able to take those classes free of charge. Normal SSSH sessions follow the same general principles. All exercise training sessions are completed under the supervision of trained exercise personnel. The classes consist of group strength training, balance and flexibility twice a week for eight weeks. Each session begins with a 5 min warm-up period, followed by two sets of ten repetitions of eight strength exercises including, but not limited to wide leg squat, standing leg curl, knee extension, side hip raise, biceps curl, overhead press, seated row and toe stand. Exercises are subject to change and will vary with each individual as needed to ensure progression and specificity. Classes end with a 5 minute cool down period including light stretching and breathing exercises.

Participants who are assigned to the walking group will be asked to refrain from any strength training or auxiliary forms of physical activity outside of the designated walking group. Two times per week SSSH personnel will guide these walking groups for about 45 minutes of total exercise time. Participants who complete the study will be automatically enrolled in the next SSSH program free of charge.

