Participants who are assigned to the sedentary control group will be asked to refrain from any strength training or auxiliary forms of physical activity for the duration of the study. Participants who complete the study will be automatically enrolled in the next SSSH program free of charge.

Statistical Analysis- All data will be tested for normality. Baseline characteristics will be assessed using a one-way ANOVA. A repeated measures ANOVA with between and within effects will be used to track physiological changes over time in each group. Pearson's correlations will be used to better understand relationships between variables. Rates of change will also be calculated and will be assessed using t-tests.

Potential Risks/Adverse Events

The research team has taken extensive measures to reduce risk and the potential for adverse events. Both participant and research staff safety are a priority. We will minimize these risk by taking the following precautions:

- Standard aseptic technique will be used for drawing blood and only trained personnel will complete blood sample, DXA scans, and functional testing.
- This research does not involve vulnerable populations and we are not collecting any highly sensitive personal or medical information (e.g. social security numbers, banking information, HIPAA information) and do not expect any of the collected data to impact a participant's employment, insurability, social status, or reputation if it were to become public.
- Subjects' information will be coded and will be stored on University of Missouri secure database and we will follow a strict protocol to ensure patient confidentiality at all times.
- Subjects are asked to perform balance assessment tests close to a wall under the supervision of trained personnel to avoid falls. Trained research staff will always be within reach to aid a participant if they lose their balance. Participants will never be left alone to complete a task.

Any serious adverse events will be reported directly to the IRB, please see the Data Safety Monitoring Plan below for more details. In case of emergency, the electromyography, dual x-ray absorptiometry, or blood drawing process will be immediately stopped. We will dial 911 in the case of emergency.

Anticipated Benefits

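### With two visits, the planned repeated measures ANOVA compares completers' change scores without conditioning on baseline: less precise than ANCOVA, and open to bias if dropout is uneven between arms and related to baseline

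*Combined protocol and SAP*

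**What the plan says.** The analysis plan is one paragraph (Statistical Analysis). For the outcomes it states: "A repeated measures ANOVA with between and within effects will be used to track physiological changes over time in each group". It adds: "Rates of change will also be calculated and will be assessed using t-tests".

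The arms are formed by randomisation. Staff will "randomize the participants into either the experimental group, walking group, or sedentary group" (Study Procedures/Design/Treatment Plan), and the primary objective is a comparison of SSSH with the walking and sedentary groups.

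There are two outcome visits and none in between: "These two visits lasting 2 hours each will occur immediately before and after the eight week intervention period".

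On losses, Number of Subjects says "We believe nearly 50 participants total are needed to reach statistical power for this study" and then "assuming 15% attrition rates, 60 participants (up to 20 per group) will be recruited for the study". Under Visit I, participants are told that "participation is completely voluntary and can be terminated at any time for any reason".

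The plan names no analysis population, no method for missing data and no sensitivity analysis. It does not say whether someone who stops attending is still asked to Visit III. It does not state a completers-only analysis either; that follows from the method named.

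**The concern.** With one value before and one after, the group-by-time test of a repeated measures ANOVA is the same test as a one-way ANOVA of the change scores. A participant without Visit III has no change score and drops out of it. The t-tests on rates of change have the same limit.

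Two consequences follow.

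- **Precision.** A change score gives the baseline value a fixed weight of one, whatever the correlation between visits. ANCOVA estimates that weight and so does as well or better, apart from the small cost of estimating it. This holds whether or not anyone drops out.
- **Bias.** People who start low tend to rise at the second measurement and people who start high tend to fall. If one arm loses more of its weaker participants, its completers start higher and their change is smaller, with no treatment effect involved.

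Selective loss is plausible. Participants know their assignment, the arms ask for very different effort, and the trial admits people who use a cane or walker. The documents give no dropout by arm, so this remains a possibility and not a finding.

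**Working it through.** **1. The plan's own figure.** Inflating 50 for 15% attrition: 50 / (1 − 0.15) = 58.8, so 59, or 60 for three equal groups. The target of 60 reproduces. Expected losses are 60 × 0.15 = 9, leaving 60 × 0.85 = 51, about 17 per arm, against the nearly 50 said to be needed. The allowance therefore covers the loss in numbers.

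**2. Inputs for the rest.** From the documents: two visits, up to 20 per arm, 15% attrition overall. Assumed, because the documents do not give them: pre/post correlation ρ of 0.5, 0.7 or 0.9; dropout of 25% in one arm and 5% in the other (mean 15%); the strength of the link between dropout and baseline. The outcome SD is set to 1 at each visit, with higher meaning better, and there is no true effect.

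**3. Precision, in closed form.** The variance of a change score is 2(1 − ρ). The residual variance after baseline adjustment is 1 − ρ². Their ratio is (1 + ρ)/2, which is 0.75, 0.85 and 0.95 at the three correlations. With 15 and 19 completers, √(1/15 + 1/19) = 0.345.

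| ρ | SE, change score: √(2(1 − ρ)) × 0.345 | SE, adjusted: √(1 − ρ²) × 0.345 | Simulated (change / adjusted) |
|---|---|---|---|
| 0.5 | 0.345 | 0.299 | 0.339 / 0.306 |
| 0.7 | 0.267 | 0.246 | 0.268 / 0.254 |
| 0.9 | 0.154 | 0.150 | 0.157 / 0.157 |

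The simulation used 12,000 replicates. Its adjusted figures are slightly above the formula because the slope has to be estimated and completers' baselines differ. At ρ = 0.5 the variance ratio is (0.306/0.339)² = 0.81. The gain at 0.5 and 0.7 remains when dropout is equal between arms or unrelated to baseline.

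**4. Bias from baseline-related dropout, in closed form.** Given baseline b, the expected change is −(1 − ρ)b. If completers in one arm start higher by a gap Δ, the change-score difference is −(1 − ρ)Δ. In the simulation, dropout followed a logistic model with slope −1.5 per baseline SD, set to 25% v 5%. That leaves Δ of about 0.21 SD:

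- ρ = 0.5: 0.5 × 0.21 = 0.105 (simulated 0.109)
- ρ = 0.7: 0.3 × 0.21 = 0.063 (simulated 0.062)
- ρ = 0.9: 0.1 × 0.21 = 0.021 (simulated 0.019)

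These are absolute sizes. The sign goes against the arm that loses its weaker participants. The adjusted estimates were 0.002, −0.001 and −0.002.

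**5. How far this depends on the assumptions.**

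- Unequal dropout unrelated to baseline: bias about 0.
- Equal 15% dropout with the same link to baseline in all arms: bias about 0.
- 25% v 5% with a weaker slope of −0.5: about 0.04 (0.05 in a repeat run), 0.03 and 0.01 SD at the three correlations.
- 20% v 10% with slope −0.5: about 0.02 SD or less.
- A sharper rule that mostly removes the lowest baselines, at ρ = 0.5: −0.14 SD for 25%/15%/5% dropout in SSSH/walking/sedentary and −0.17 SD for 30%/10%/5%, SSSH minus sedentary. Adjustment brings both to within 0.01 of zero.

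**6. Dropout related to the outcome.** If those with poor change leave, at ρ = 0.5, the 30%/10%/5% pattern gives +0.33 SD in favour of SSSH, and adjustment lowers it only to +0.27. For 25%/15%/5% the figures are +0.27 and +0.22.

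**The case against.** The strongest reply is that the effect is small and rests on assumption. Only the 15% and the 20 per arm come from the documents; the split, the slope and the correlations do not. Even 0.109 SD is about a third of its own standard error (0.109/0.339 = 0.32), and in that scenario the type I error was 0.060, 0.058 and 0.050 at the three correlations. If weaker participants leave SSSH, the error works against the intervention. Completion is also rewarded: completers receive $100 (Compensation), and walking and sedentary participants who complete get a free place in the next class. Visit III is not made conditional on attendance. All of this stands, and it limits the bias argument. It does not touch the precision argument, which needs no dropout at all.

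A reader might go further in four ways that the documents do not support.

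- **Uneven dropout by itself biases the comparison.** It does not; it must also be related to baseline or outcome.
- **The 9 expected losses leave the trial short.** The allowance was made for them: 51 against nearly 50.
- **A mixed model would bring the 9 back.** With two visits, a participant with baseline only adds almost nothing to the between-arm contrast. The gain comes from conditioning on baseline.
- **The plan excludes non-attenders or moves them to another arm.** It says nothing on this.

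**Conclusion.** The point holds as a choice of analysis that can be improved at almost no cost. The two-visit ANOVA, and the t-tests where they compare arms, are complete-case comparisons of change that ignore information in the baseline value.

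The loss of precision is about 10% of the standard error at correlation 0.5 (0.339 v 0.306), about 5% at 0.7 (0.268 v 0.254) and nothing useful at 0.9. The possible bias from uneven, baseline-related dropout is about 0 to 0.11 SD under the logistic model with 25% v 5%. It is larger only under sharper selection (0.14 to 0.17 SD). Its direction is against the arm that loses its weaker participants.

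All of these sizes rest on assumed correlations and dropout patterns. Outcome-related dropout could do more harm, and baseline adjustment leaves most of it in place. The change should be made, but nothing here shows that the trial as planned would give a wrong answer.

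**What to change.** In Statistical Analysis, replace the between-arm use of the repeated measures ANOVA and of the rate-of-change t-tests with text to this effect: each outcome is compared between arms by ANCOVA of the Visit III value, with the Visit II value as covariate and assigned arm as factor. Participants are analysed in the arm to which they were randomised, whatever their attendance. A mixed model of both visits with a common baseline mean is a near-equivalent alternative. Within-group changes can still be reported descriptively.

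Three additions are needed:

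- Under Visits II & III, state that participants who stop attending, and are willing, are invited to Visit III.
- Report the number without Visit III by arm, with their baseline values.
- Prespecify a simple sensitivity analysis for outcome-related dropout, for example shifting the imputed Visit III values of dropouts by a range of amounts, separately by arm, and reporting where the conclusion changes.

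The cost is a little more analysis work in standard software and a few extra Visit III contacts. No new measurement is needed, and the sample size does not change.

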In order to protect the participants' personal information, data, and right to privacy this research team will take extensive precautions to maintain confidentiality. After the participant has cleared the initial screening forms and signed the informed consent all remaining surveys, questionnaires, DXA results, blood samples, and data sheets will only contain the participant' identification code. The key linking names and participant identification codes will be accessible to [name] and she will only share the key with the research team once unblinding is necessary. All paper records will be kept in a locked filing cabinet in [name] MU office (she is a Professor and Director of Orthopaedic Research and is familiar with handling confidential documents). Computerized records of experimental data will be similarly coded and will be maintained on a password protected MU secure computer. Copies of signed consent forms, as well as the experimental log book, are kept in a locked file cabinet in [name] office. Participants will not be individually identified in any publications.

Additionally, all adverse events and/or unanticipated problems will be evaluated by Drs. [name], [name], and [name] as they occur, for subject safety and appropriate follow-up assessment, treatment, or care. All adverse events and/or unanticipated problems will be evaluated and assessed to answer the following questions: Is the event unexpected? Is the event related or possibly related to participation in the research? Does the event suggest that the research places subjects or others at a greater risk of harm than previously known or recognized? If all three answers are “yes”, the event will be reported to the IRB within 5 days of the investigator becoming aware of the event. While reviewing each event, the PI(s) will determine if it is safe for the subject to continue participating in the trial and if it is safe to continue enrollment and research activity for all subjects.

Multiple Sites

University of Missouri is the only site where research activities will occur. All required approvals are in order for the three specific rooms where data will be collected and analyzed.

References/Appendices

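### Does the Data Safety Monitoring Plan leave some serious adverse events without a route to the IRB?

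*Combined protocol and SAP*

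**What the plan says.** Two places in the protocol deal with reporting to the IRB.

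- **Potential Risks/Adverse Events** makes the commitment on serious events: "Any serious adverse events will be reported directly to the IRB, please see the Data Safety Monitoring Plan below for more details". It sets no condition and no deadline.
- **Data Safety Monitoring Plan** opens with confidentiality and then turns to events. Every event is reviewed when it happens: "All adverse events and/or unanticipated problems will be evaluated and assessed to answer the following questions: Is the event unexpected". The other two questions are "Is the event related or possibly related to participation in the research" and "Does the event suggest that the research places subjects or others at a greater risk of harm than previously known or recognized". When all three are answered yes, "the event will be reported to the IRB within 5 days of the investigator becoming aware of the event". For each event reviewed, "the PI(s) will determine if it is safe for the subject to continue participating in the trial", and the same judgement is made about continuing enrolment and the research as a whole.

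Seriousness is not one of the three questions. The word serious is applied to an event only once in the document, in the commitment above, and it is not defined.

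**The concern.** The first section sends the reader to the second for the details on serious events, and the second has none that are specific to them. Someone who opens only the Data Safety Monitoring Plan finds a narrower test. A serious event judged expected, unrelated, or uninformative about new risk meets no reporting rule there and has no time limit.

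If staff worked from that section alone, such an event might never reach the IRB, despite the commitment made elsewhere. An injurious fall during balance testing is a conceivable example, if the study team regarded falls as expected. The protocol lists no expected events, so this cannot be settled either way. The stake is outside oversight of participant safety, in sedentary adults aged 60 or over, some of whom may use a cane or walker.

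**Working it through.** No figure in the plan needs reproducing here. The check is whether the two sections can both be obeyed, and what is left unstated when they are.

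**Inputs**

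- Rule A (Potential Risks/Adverse Events): if an event is serious, report it to the IRB. No condition, no deadline.
- Rule B (Data Safety Monitoring Plan): if all three answers are yes, report the event to the IRB within 5 days. Seriousness plays no part.
- Scope of Rule B's review: all adverse events, and therefore serious ones too.

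**Step 1. Are the rules compatible?** Rule B is a sufficient condition for reporting. It is worded with if, not only if, and nothing in the section says that events failing the test are not to be reported. Rule A is also a sufficient condition. Two sufficient conditions for the same action cannot conflict. An event is reported when it meets either.

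**Step 2. Apply both to a serious event.** Three yes/no questions give 2 × 2 × 2 = 8 answer patterns.

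| Answers | Patterns | Report under A | Report under B | Deadline stated |
|---|---|---|---|---|
| All yes | 1 | Yes | Yes | 5 days |
| At least one no | 7 | Yes | Not triggered | None |

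A serious event is reported in 1 + 7 = 8 of 8 patterns. The deadline is unstated in 7 of 8. These are counts of patterns, not probabilities.

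**Step 3. What would an amendment add?** Repeating Rule A inside the Data Safety Monitoring Plan leaves the count at 8 of 8, so it adds 8 − 8 = 0 reports to what the protocol already requires. The only new content would be a deadline for the seven patterns. The documents supply no basis for choosing one.

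**Step 4. How many events might be involved?** The documents give no event rates. Purely as an assumption, let each of the 60 planned participants ("60 participants (up to 20 per group) will be recruited for the study") have a risk p of a serious event, with p between 1% and 5%. The expected number of participants with such an event is 60p, and the chance of at least one is 1 − (1 − p)^60.

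- p = 0.01: 60 × 0.01 = 0.6 expected; 1 − 0.99^60 = 45.3%.
- p = 0.02: 60 × 0.02 = 1.2 expected; 1 − 0.98^60 = 70.2%.
- p = 0.05: 60 × 0.05 = 3.0 expected; 1 − 0.95^60 = 95.4%.

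These are averages and chances under an assumed rate, not ceilings, and the share with at least one no answer is unknown. The conclusion does not rest on them.

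**Step 5. Does any result depend on it?** The Statistical Analysis section covers normality checks, ANOVA at baseline and over time, correlations, and t-tests on rates of change. None of these uses IRB reports or their timing.

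**The case for a change.** The best argument for a change is that a cross-reference should lead somewhere. The protocol names the Data Safety Monitoring Plan as the place for details, and staff under pressure will go there. The three questions are answered within the study team, so a no removes the only reporting rule that section contains. Internal review of every event is useful, but it is not the IRB report that was promised. The missing text is not a result of redaction either, since only names are removed from that part of the document. One or two sentences would tidy it up.

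Much of this stands. The cross-reference is incomplete, serious is undefined, and a serious event with any no answer has no stated deadline. What does not stand is the step from there to unreported events. That requires staff to apply one section and disregard a plain, unconditional sentence in the other. Nor are serious events outside the monitoring plan: they are reviewed as they occur, considered for follow-up care, and put through the decision on continuing. The fall example is speculative, and the protocol takes steps against it: "Subjects are asked to perform balance assessment tests close to a wall under the supervision of trained personnel to avoid falls", with staff within reach.

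**Conclusion.** The observation about the text is accurate, but it is a gap in detail and not a conflict. Read together, the two sections require an IRB report for every serious adverse event and a safety review of every event. The unstated item is a deadline in seven of the eight answer patterns, which the study team can settle with the IRB when it reports. Repeating the commitment in the second section would add no reports to those already required, and no estimate, test or conclusion of the trial would alter.

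This rests on two readings: that the three-question rule is not exclusive, as its wording indicates, and that the commitment on serious events applies as written. If the study team in fact treats three yes answers as the only route to the IRB, its practice would depart from its own protocol. The remedy would then be to follow the protocol as it stands.
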